11.2.1 Period of Collection

All existing health conditions identified during the Screening Period will be recorded as concomitant disease and the participant's eligibility will be reviewed. Any AEs which occur during the screening session will be captured by the study site staff and assessed by the Investigator or designee in order to establish relationship or relatedness in respect to study procedures.

Any new, clinically relevant, abnormal finding detected during the study or worsening of a pre-existing condition/concomitant disease will be documented as an AE or an SAE.

11.3 ASSESSMENT OF ADVERSE EVENTS

11.3.1 Intensity of Adverse Events

For each AE/SAE, the intensity will be graded on a 3-point intensity scale:

- Mild: The AE is easily tolerated and does not interfere with daily activity.
- Moderate: The AE interferes with daily activity, but the participant is still able to function.
- Severe: The AE is incapacitating and requires medical intervention.

11.3.2 Relationship to Study Procedures

In general, all AEs and SAEs will be assessed by the Investigator or designee as either 'related' or 'not related'.

- Not related: The temporal relationship of the clinical event to study procedures and/or the study medication makes a causal relationship unlikely, or, concomitant medication, therapeutic interventions, or underlying conditions provide a sufficient explanation for the observed event.
- Related: The temporal relationship of the clinical event to study procedures and/or the study
 medication makes a causal relationship possible, and concomitant medication, therapeutic
 interventions, or underlying conditions do not provide a sufficient explanation for the
 observed event.

11.4 FOLLOW-UP OF NON-SERIOUS AND SERIOUS ADVERSE EVENTS

Non-serious AEs will not be followed-up by the Investigator or designee after the end of study. The Investigator or designee will refer the participant to their Primary Care Provider for follow up of those AE(s) until they have resolved, stabilized (i.e., no worsening of condition), or until an acceptable explanation has been found.

Serious AEs will be followed up by the Investigator or designee, despite their continuation after the end of study, until their resolution, stabilization (i.e., no worsening of the condition), or an acceptable explanation has been found (e.g. a chronic condition).

11.5 REPORTING OF SAFETY EVENTS TO IRB

The Principal Investigator will report all serious adverse events relating to the study in an expedited manner to the Institutional Review Board (IRB) office in accordance with the Center's standard operating procedures and GCP reporting guidelines.

11.6 Reporting of Safety Events to FDA

The Principal Investigator will report any suspected adverse reaction to study treatment that is both serious and unexpected to the FDA following established Safety Reporting guidelines.

11.7 REPORTING AND FOLLOW-UP OF PREGNANCIES

All participants who are determined to be pregnant after enrollment will be discontinued from the study. Advice on the risk of smoking and smoking cessation will be provided by the study doctor (or qualified staff) and participants will be referred to the respective health care facility/health care provider for further support.

The Investigator is responsible for informing the IRB of any pregnancy that occurs during the study, and its outcome, according to local regulations.

11.8 Adverse Event Leading to Discontinuation

If a participant is discontinued from the study because of an AE, the Investigator or designee will follow up until the AE(s) has/have been resolved, stabilized (i.e., no worsening of condition), or until an acceptable explanation has been found.

12 DATA MANAGEMENT

12.1 DATA COLLECTION PROCEDURES

Trained study personnel will be responsible for capturing the data from the observations, tests, and assessments specified in the protocol and in the source documents.

The Investigator has ultimate responsibility for the collection and reporting of all data related to the clinical study and ensuring that the data are accurate, authentic/original, legible, timely (contemporaneous), enduring, and available when required. Any corrections made to source documents

must be clearly recorded, without obscuring the original values and be accompanied by the date of change and identification of the person making the change.

Study staff will maintain appropriate medical and research records for this study, in compliance with ICH E6, Section 4.9 and regulatory and institutional requirements for the protection of confidentiality of participants. Study staff will permit authorized representatives and regulatory agencies to examine (and when required by applicable law, to copy) research records for the purposes of quality assurance reviews, audits, and evaluation of the study safety, progress and data validity.

12.2 PROTOCOL DEVIATIONS / NONCOMPLIANCE

Protocol deviations are defined as deviations from the study procedures as defined in this document, whether intentional or unintentional that may affect the participant's rights, safety, or well-being and/or the completeness, accuracy and reliability of the data.

Noncompliance that meets the above definition must be reported to the IRB within 10 days of becoming aware of the noncompliance.

12.3 DATA CAPTURE

All data are collected from participants using paper documents or an electronic data capture system. All applicable data, as specified in the protocol, will be transferred to the database or applicable Case Report Forms.

12.3.1 Salesforce.com

Data will be collected for recruitment and screening purposes as stated within an Advarra IRB generic recruitment protocol. Unrelated to that protocol, pre-screening questionnaires will be attached to potential participant's records on whether they qualify or are disqualified for this study. Questionnaires utilized for this study will be permanently attached to that potential volunteer's record unless that information is requested to be removed by the participant.

12.3.2 Survey Monkey

Survey Monkey uses some of the most advanced technology for Internet security that is commercially available today. This Security Statement is aimed at being transparent about our security infrastructure and practices, to help reassure that data is appropriately protected. Visit Survey Monkey privacy policy for more information on data handling.

All Survey Monkey information systems and infrastructure are hosted in world-class data centers. These data centers include all the necessary physical security controls you would expect in a data center these days (e.g., 24×7 monitoring, cameras, visitor logs, entry requirements). SurveyMonkey has dedicated cages to separate our equipment from other tenants. In addition, these data centers are SOC 2 accredited.

12.3.3 Short Message Service (SMS) Messaging

SMS Messaging will be utilized for the delivery of a hyperlink to a mobile device to collect study data. This data will be collected utilizing an electronic survey. The service utilized for these messages is textit.in.

12.3.4 Medrio

All smoking behavioral and self-report measures will be captured initially using Medrio. Medrio is an electronic data collection system that records and performs analysis and reporting of data. Participant data will be kept within Medrio's secure servers and may only be transmitted through a secure (SSL) download to our local server. Medrio's servers are protected by high-end firewall systems, with vulnerability scans performed regularly. All services have quick failover points with redundant hardware, and complete encrypted backups are performed regularly. Medrio uses Transport Layer Security (TLS) encryption (SSL or HTTPS) for all transmitted internet data. All information collected within Medrio is compliant with 21 CFR 11 requirements.

12.4 Missing Data

Missing data will remain as missing, i.e., no attempt will be made to impute missing values and only observed values will be used in data summarizations and analysis.

12.5 DATA HANDLING

Data of all participants enrolled including screening failures and AE/SAEs during the study (from the time of informed consent to the end of the study of the participant) will be captured in the source documents.

12.6 DATA VALIDATION

Data that are entered will be verified and edit checked to ensure accuracy. Inconsistencies that arise from these checks will be resolved and documented by study staff.

12.7 DATABASE LOCK

Upon completion of the trial, after data entry is complete, the data has been cleaned, and the principal investigator has reviewed and provided approval, the database will be locked, and final write access will be removed.

13 PLANNED STATISTICAL METHODS

All data measures (e.g., withdrawal symptoms questionnaires, smoking history, smoking diaries, etc.) are captured initially using paper or an electronic data capture system. Verified data files will be analyzed using Statview or SAS (Statview, SAS Institute, Cary NC). Data will be inspected for outliers and if sufficiently extreme (Chauvenet's criterion, after verifying normality of distributions) will be censored from the data analysis.

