13.1.2 Side Effects / Tolerability

The hypothesis that hydroxyzine reduces the incidence of nausea, one of the most common side effects of varenicline, will be evaluated by comparison to the benchmark of 30% (20% above placebo rate of 10%) observed in clinical trials of varenicline.³⁶ Initially, 25 participants will be recruited and then the possibility of recruiting 25 more (total N=50) depending on an interim analysis, as follows:

- If 0-3 participants out of 25 (12% or less) report nausea, we would conclude the treatment is highly promising at the interim stage and go directly to an RCT (Branch 1).
- If 4-6 participants (out of 25) report the side effect, then the treatment will be deemed sufficiently promising to recruit an additional 25 participants (Branch 2). If 10 or less of the total 50 report the side effect of nausea (20% or less), a follow-up RCT would be warranted; otherwise the treatment would be deemed unpromising.
- If 7 or more out of 25 (28% or more) report the side effect of nausea in the interim analysis, then we would conclude it is futile to continue the pilot and the study would be terminated (Branch 3).

The frequency of treatment-emergent side effects (i.e., those that begin or worsen after the initiation of treatment) will be tabulated. Due to the problem of Type II error posed by significance testing numerous side effect outcomes (especially if corrections are imposed for multiple comparisons), descriptive statistical methods will instead be used, supplemented by calculation of confidence intervals and p-values as a flagging device to highlight differences worthy of further attention.³⁷ Hypothesis testing will be conducted for only two outcomes: 1) proportion of participants that withdraw from the study due to side effects; 2) overall adherence (i.e., proportion of scheduled doses taken) assessed by daily medication diaries and returned capsules.

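### Section 13 removes verified values by Chauvenet's criterion without evidence of error; even after a normality check about a third of clean normal variables lose a genuine value, and 95% coverage falls to about 93%

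*Combined protocol and SAP*

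**What the plan says.** Section 13 sets one outlier rule for the whole analysis: "Data will be inspected for outliers and if sufficiently extreme (Chauvenet's criterion, after verifying normality of distributions) will be censored" from the analysis. I read this as exclusion of the value. The section names no variables, no normality test and no number of passes. It does not say what happens to a variable that fails the normality check, and it provides no companion analysis with every value kept.

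The rule acts on files that have already been checked. The sentence before it reads "Verified data files will be analyzed using Statview or SAS", and Section 12.6 says "Data that are entered will be verified and edit checked to ensure accuracy". Section 12.4 adds that "no attempt will be made to impute missing values and only observed values will be used in data summarizations and analysis", so a removed value is simply lost.

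The samples are small. Section 13.1.2: "Initially, 25 participants will be recruited and then the possibility of recruiting 25 more (total N=50) depending on an interim analysis". The same section plans to tabulate side effects, "supplemented by calculation of confidence intervals and p-values as a flagging device to highlight differences worthy of further attention", and reserves hypothesis testing for two outcomes. One of these is quantitative: "overall adherence (i.e., proportion of scheduled doses taken) assessed by daily medication diaries and returned capsules". Sections 2.2 and 2.3 also plan to correlate pre-quit smoking reduction and other early measures with abstinence.

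**The concern.** An outlier rule is defensible when it catches errors. This one asks only whether a value is far from the mean, and Chauvenet's threshold is set so that about half a value per sample is expected beyond it when nothing is wrong. A normality check does not help, because the rule misfires on data that really are normal.

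Removing genuine tails shrinks the SD, so confidence intervals come out too narrow and p-values too small. Where a measure is skewed but still passes the check, the mean is also pulled. In a single-arm study of 25 to 50 people, losing one or two informative values per measure can matter for adherence, questionnaire scores and the smoking-reduction correlations. The unstated number of passes and choice of test leave decisions to be made after the data are seen.

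**Working it through.** **Plan's own figures.** The documents give no deletion rate or coverage for this rule, so there is nothing to reproduce for it directly. The design figures in Section 13.1.3 were checked by exact two-stage binomial calculation: success is 3 or fewer of 25, or 4 to 6 of 25 followed by 10 or fewer of 50.
- Type I error at 30% nausea: 8.6% (stated 9%).
- Power at 15% nausea: 86.1% (stated 86%).
- Power at 10% nausea: 98.5% (stated 98%).

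These rest on counts of participants, so the outlier rule does not enter them.

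**Inputs.** From the documents: n = 25 or 50, Chauvenet's criterion, a normality check first, no imputation. Assumed: a 95% t interval for a mean, Shapiro-Wilk at 5%, sample SD with divisor n−1, one pass, and all values observed.

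**Cut-off.** A value is dropped when n × P(|Z| > z) < 0.5, that is, when z exceeds Φ⁻¹(1 − 1/(4n)).
- n=25: Φ⁻¹(0.990) = 2.33 SD.
- n=50: Φ⁻¹(0.995) = 2.58 SD.

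**Rough analytic check.** If the mean and SD were known, each clean value would be dropped with probability 0.5/n. The chance of losing at least one is 1 − (1 − 0.5/n)ⁿ, which is 39.7% at n=25 and 39.5% at n=50. Estimating the mean and SD from the same sample lowers this somewhat, hence the simulation.

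**Simulation on clean normal data.**

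| Case | Variables losing a value | Coverage of 95% interval |
|---|---|---|
| All values kept, n=25 or 50 | 0% | 95.0% |
| Check passed, one pass, n=25 | about 32% | about 92.8% |
| Check passed, one pass, n=50 | about 34% | about 93.6% |
| No check, one pass, n=25 | about 33.6% | about 92.4% |
| No check, one pass, n=50 | 35.7% | about 93.4% |
| No check, repeated passes, n=25 | about 33.5% | about 91.3% |
| Check passed, repeated passes, n=25 | about 32% | about 92% |

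Separate runs agree to within about 0.2 points either side of the coverage figures. With the check and one pass, non-coverage is 100 − 92.8 = 7.2% at n=25 and 100 − 93.6 = 6.4% at n=50, against a nominal 5%. About 0.33 values are lost per passing variable at n=25, and 0.33/25 = 1.3% of observations. The damage is concentrated: at n=25 without the check, coverage among variables that lose a value is 87.5%.

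**Mildly skewed data (assumed lognormal, sigma 0.4), n=25.** About 53% of samples pass Shapiro-Wilk. Deleting only when the check is passed lowers coverage over all samples from about 93.9% to about 91.4%, with a mean bias of about −0.9%.

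**The case against.** The strongest reply is that the harm is measured on an analysis the plan does not specify. No section calls for a t interval on a mean. The intervals and p-values in Section 13.1.2 accompany side-effect frequencies, which are proportions. Nausea, abstinence and withdrawal due to side effects are all yes/no. Adherence is the only quantitative outcome set for a test, and no test or benchmark is given for it. The rule is objective, named in advance, and used in a pilot whose decision rests on a count. All of this stands as a limit on scope. It does not make the rule harmless for the quantitative measures it does reach.

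Four stronger readings are tempting, and the documents do not support them.

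- *The rule hits every continuous measure.* It applies only after normality is verified. PHQ-9 is capped at 9 on entry (Section 4.1.2), adherence is bounded at 100%, and cigarettes and CO in abstainers sit near a floor. Such variables would probably fail the check. The gap there is that the plan does not say what happens next.
- *Every removed value must be real, since errors are already gone.* Section 12.6 covers verification and edit checks of entered data. Cigarette counts are typed by participants into SMS surveys (Sections 8.8 and 12.3.3), and a plausible mistyped number could survive. Nor do the documents show that the removed values would be the strongest responders or the worst reactors.
- *Coverage collapses to about 88% with skewed data.* A figure of 87.8% arises only within the roughly 53% of assumed lognormal samples that pass the check. In those samples coverage is already 92.4% with nothing deleted, so part of the shortfall is due to skew and selection. The figure over all samples is the fair one.
- *The go/no-go decision or stated power is compromised.* Neither uses a quantitative measure screened by this rule.

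**Conclusion.** The concern holds for quantitative outcomes. As written, Section 13 discards verified values on distance alone. Among clean normal variables that pass the check, about 32% at n=25 and 34% at n=50 lose a genuine value, and nominal 95% coverage becomes about 92.8% and 93.6%. The shortfall is about 2 points at n=25 (95.0 − 92.8 = 2.2) and 1.4 points at n=50 (95.0 − 93.6). Repeated passes, which the text does not exclude, make it worse.

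This is a moderate flaw in secondary and exploratory analyses, and it leaves the trial's main decision intact. It matters most for adherence, if that variable passes the check, and may also touch questionnaire scores and smoking-reduction measures. The sizes rest on assumptions the plan leaves open: the 95% level, a t interval for a mean, Shapiro-Wilk as the check, a single pass, and complete data. The effect on the planned correlations was not computed.

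**What to change.** Replace the outlier sentence in Section 13 with:

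> All verified values are retained in the main analysis. Values that are impossible or traced to an error are corrected or set to missing, with a record. Clearly skewed measures are analysed by rank-based or transformed methods. An analysis excluding extreme values may be shown as a sensitivity analysis only.

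For normal data this restores 95.0% coverage at both sample sizes. It also removes the undefined choices of test, passes and variables, and it says how skewed measures are handled.

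The cost is a few lines of wording and slightly wider intervals. In the simulation without the check at n=25, deletion made intervals 4.3% narrower on average, so keeping all values widens them by about 1/0.957 − 1 = 4.5%. An undetected entry error could also stay in the main analysis; the sensitivity analysis would show whether it matters.

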13.1 EFFICACY AND TOLERABILITY

13.1.1 Abstinence Outcomes

Abstinence at each time point will be defined by a self-report of no cigarette smoking (not even a puff) since the prior session, confirmed by an expired air CO reading of less than 5 ppm. The primary

abstinence outcome will be abstinence during weeks 8-11 post-quit date. An intent-to-treat approach will be taken in which any participants lost to follow-up after the point of randomization, or who have relapsed prior to the end of treatment (week 11 post-quit) will be counted as non-abstinent (in accordance with recent guidelines from the FDA). A secondary smoking abstinence outcome will be 7day point abstinence at 6 months post-quit, for participants who have not relapsed prior to the end of treatment. The main goal of the 6-month follow-up is to assess the persistence of therapeutic effects for those who do achieve end-of-treatment abstinence. This information will be helpful in determining the treatment duration in future Phase 3 clinical trials. The main hypothesis to be evaluated in this pilot study is that the incidence of varenicline-associated side effects, specifically nausea, will be diminished by co-administration of hydroxyzine, relative to historical benchmarks (see below). A one-tailed test of abstinence will be conducted, however, comparing the proportion of participants abstinent during weeks 8-11 to the historical benchmark of 45% abstinence, to provide evidence that abstinence is not significantly lower than it would be with varenicline alone. There is no reason to expect that abstinence rate would be reduced by hydroxyzine; if anything, abstinence would be expected to be enhanced by amelioration of varenicline-associated side effects and by potential effects of H1 antagonists to reduce nicotine reward.35

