8.5 Post-Quit Sessions (V4-V7)

Sessions scheduled after the quit-smoking date will be conducted at 2 weeks after the quit date and then at 4-week intervals until the end of the 12-week treatment period. The sequence of the following assessments will be at the discretion of the Investigator or designee.

- Document concomitant disease and medication changes
- Physical examination (if indicated)
- Expired air CO breath test
- Vital signs (blood pressure, heart rate, respiratory rate)
- Weight
- Brief review of smoking cessation counseling (if indicated)
- Urine pregnancy test (all females)
- Collection and dispensing of study drugs (collection only at the EOS visit)
- Assess medication compliance
- Verification of proper use of the SMS messaging (refresher training, if needed)
- Questionnaires
 - o FTND
 - o PSS-10
 - MNWS
 - o 6-Item STAI
 - o Adverse Effects Questionnaire
 - Patient Health Questionnaire (PHQ-9)
 - Smoking Status (review with participant and continue daily via SMS survey until End of Study)
 - Medication Compliance (review with participant and continue daily via SMS survey until End of Study)

8.6 6-Month Follow Up

Participants who successfully complete the study and are abstinent at the final visit (V7), will be contacted six months after the quit day utilizing an automated SMS messaging system, to ascertain their current smoking status.

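### The six-month abstinence outcome cannot meet the plan's own CO-confirmed definition, and the plan has conflicting rules for an unanswered six-month text

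*Combined protocol and SAP*

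**What the plan says.** Section 13.1.1 gives one definition for all time points: "Abstinence at each time point will be defined by a self-report of no cigarette smoking" since the previous session, "confirmed by an expired air CO reading of less than 5 ppm". The same paragraph adds: "A secondary smoking abstinence outcome will be 7day point abstinence at 6 months post-quit", restricted to those still abstinent at the end of treatment ("for participants who have not relapsed prior to the end of treatment"). The stated aim is to see whether the effect lasts in people who reach end-of-treatment abstinence, and to help choose the treatment duration in later trials.

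Section 8.6 supplies the data. Participants who complete the study and are abstinent at V7 "will be contacted six months after the quit day utilizing an automated SMS messaging system, to ascertain their current smoking status". In the Section 8.7 schedule the six-month column is marked for smoking status and not for the CO breath test. Section 7.2.5 places CO testing at the laboratory sessions.

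Two rules bear on missing replies. Section 12.4 rules out imputation, and says "only observed values will be used in data summarizations and analysis". Section 13.1.1 takes an intent-to-treat approach: people lost to follow-up after randomization, or relapsed before the end of treatment at week 11 post-quit, count as non-abstinent.

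**The concern.** An outcome should be obtainable from the data that the plan collects. Here the definition needs a breath sample and the procedure sends a text message. Read literally, nobody can be classed as abstinent at six months. In practice someone will have to relax the definition, and the plan does not say so or say how the result will be labelled.

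The missing-reply question matters because the denominator is small and the contact is a single automated message sent some months after the last visit. If silent participants leave the denominator, the persistence rate describes only those who answered. If they count as smoking, it describes everyone who was abstinent at the end of treatment. With no governing rule stated, that choice could be made after the replies have been seen.

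**Working it through.** The documents give no six-month rate, response rate or sample size, so there is no stated figure to reproduce. The check has two parts.

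**1. Can the outcome meet the definition?**

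- Required at each time point: self-report plus CO below 5 ppm (13.1.1).
- Where CO is measured: laboratory sessions (7.2.5), which the schedule marks at V1 to V7 with nothing at six months (8.7).
- What six months provides: an automated text (8.6) with two questions, on any cigarette since the last visit and on smoking right now (8.8.3, Appendix 19).

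The CO component is therefore never observed at six months. This needs no assumption.

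**2. Which rule covers an unanswered text?**

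- Section 12.4 is general. Applied here, it removes the non-responder.
- The 13.1.1 clause is specific to abstinence and puts no end date on loss to follow-up. Its starting point is a randomization that this single-group study does not have.
- Section 4.5 makes the lost-to-follow-up date the participant's end-of-study date. Section 5.5.1 identifies end of study as Visit 7 or early termination. Section 8.6 texts only people who have completed. Section 3.4 puts total participation at about 14 to 16 weeks.

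Someone who ignores the six-month text has already completed the study, so does not naturally fall under loss to follow-up. Section 12.4 plausibly governs, but the text does not settle it.

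**Size of the difference.** Let E be the end-of-treatment abstainers who are texted, R those who reply, and A those who report abstinence.

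- Observed values only: A/R.
- Non-responders counted as smoking: A/E.
- Ratio of the two: (A/R)/(A/E) = E/R = 1/(response rate).

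Taking 60% of responders reporting abstinence (assumed), and a range of assumed response rates:

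| Response rate | Ratio | Observed only | Non-response as smoking |
|---|---|---|---|
| 100% | 1.00 | 60% | 60% |
| 90% | 1/0.9 = 1.11 | 60% | 0.60 × 0.9 = 54% |
| 80% | 1/0.8 = 1.25 | 60% | 0.60 × 0.8 = 48% |
| 70% | 1/0.7 = 1.43 | 60% | 0.60 × 0.7 = 42% |

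In counts, the 45% benchmark in 13.1.1 gives 0.45 × 25 = 11.25, about 11 people, or 0.45 × 50 = 22.5, about 22. If 18 of 22 reply and 9 report abstinence (assumed), the two rules give 9/18 = 50.0% and 9/22 = 40.9%.

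Missing CO confirmation could add to this. If a share f of positive self-reports would fail a CO test, the unverified rate is higher than the verified one by 1/(1 − f), which is 1.11 at an assumed f of 10%. The documents give no value for f.

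**The case against.** The strongest reply on the definition is that it is built around sessions: it refers back to the previous session, and CO is a session measurement. The six-month outcome has its own seven-day definition and no session, so the reference to each time point may simply be loose drafting. That is a fair account of how the wording arose. It does not remove the contradiction, because nothing in 13.1.1 exempts the six-month time point.

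On missing replies, the end-of-treatment limit in 13.1.1 can be read as attaching only to relapse, leaving loss to follow-up open-ended. An abstinence-specific rule could then override the general one in 12.4. This stands to the extent that a reader cannot conclude that the plan definitely drops non-responders. What remains is a conflict.

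A reader might also infer that persistence is overstated. The documents do not show that. They contain no response or misreport rate, and the 1/(response rate) factor is the distance between two conventions, equal to bias only if every non-responder has relapsed. The direction is not guaranteed either: scoring the first text question alone, on any cigarette since the last visit, would be stricter than seven-day abstinence and could understate it.

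Two further inferences fail. Restricting the outcome to end-of-treatment abstainers is the declared target and not a defect. And the plan proposes no formal comparison of the week-11 rate with the six-month rate, so there is no such comparison to call invalid.

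**Conclusion.** The point holds on two counts. The six-month outcome cannot meet the CO-confirmed definition in 13.1.1, which follows directly from the text. The handling of an unanswered six-month text is unresolved between 12.4 and 13.1.1, with 12.4 the more plausible default.

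The possible effect on the reported rate is conditional. If 12.4 is applied and all non-responders have relapsed, the rate is too high by 1.11 at 90% response and by 1.43 at 70%. If everyone replies truthfully, there is no bias. With only about 11 or 22 people eligible at the benchmark rate, a few silent phones would visibly move the figure.

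The importance is moderate. This is a secondary outcome with no decision rule attached, and the go/no-go rule rests on nausea alone. It is still worth correcting, because the plan intends the result to inform treatment duration in later trials.

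**What to change.** In Sections 13.1.1 and 8.6:

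- Define the six-month outcome as self-reported and not CO-verified, and exempt it explicitly from the CO requirement that otherwise applies at each time point.
- State that an unanswered six-month text counts as non-abstinent, with all end-of-treatment abstainers as the denominator, and that this overrides Section 12.4 for this outcome.
- Report the responders-only rate beside it as a sensitivity figure, with the number who replied.

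While editing, the sponsor should also reconcile the seven-day window in 13.1.1 with the survey, since neither question in 8.8.3 or Appendix 19 asks about the past seven days.

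The main changes cost wording only: no added visit, sample or participant. The drawback is that the six-month figure may be less favourable. Counting silence as smoking is itself a conservative convention, which is why the responders-only rate should be shown alongside.
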